APPENDIX C: ATEZOLIZUMAB EXPANSION SCHEDULE OF ASSESSMENTS

1 cycle = 3 weeks	Each Cycle	EOT (30 days) ¹	Response Follow- Up (quarterly) ²	Survival (3 years) ³
Physical Exam		Х		
Symptom-Directed Physical Exam ⁴	Х			
Performance Status (ECOG)	Х	Х		
Vital Signs (including weight)	X ⁵	Х		
Toxicity (AESI/SAEs)	Х	Х		
Concomitant Medications	Х	Х	X ⁶	X ⁷
Radiological Tumor Assessment ⁸	X ⁹	X ¹⁰	X	
Triplicate ECG (recommended)	Recommende checkpoin	ed per use with t inhibitors ¹¹		
CBC with differential	Х	Х		
Serum Chemistry ¹²	Х	Х		
TSH (recommended)	Recommende checkpoin	ed per use with t inhibitors ¹³		
Immune Function Analysis ¹⁴	Х	Х		
Atezolizumab Administration ¹⁵	Х			
CA-125 ¹⁶	Х	Х	X	X
Tumor Biopsy ¹⁷	Х	X		
Phone Contact				X

² Subjects that discontinue study treatment before disease progression will have radiological assessment of disease quarterly until disease progression.

¹ End of Treatment visit will occur 30 days (+ 5 days) after the last treatment or prior to commencement of subsequent treatment.

³ Assessment performed annually after disease progression.

⁴ Symptom-Directed Physical Exam performed by a medical provider.

⁵ Vítal signs (heart rate, respiratory rate, blood pressure, temperature, and O₂ saturation) should be obtained within 60 minutes prior to atezolizumab infusion.

⁶ Collect any post study therapies taken after participation in the study.

⁷ Collect any post study therapies taken after participation in the study.

⁸ Radiological Tumor Assessment to include chest, abdomen, and pelvis. Assessment will be done per RECIST criteria for measurable disease.

⁹Radiological Tumor Assessment will be performed every third cycle.

¹⁰ Radiological Tumor Assessment performed at End of TX if not done within the previous 45 days.

¹¹Due to potential risk of myocarditis associated with atezolizumab use, it is recommended that cardiac function be monitored prior to and periodically during treatment with atezolizumab. Triplicate ECGs performed periodically during treatment with atezolizumab may help identify potential cardiac events; however, Institutional standard practice for monitoring cardiac function during use of checkpoint inhibitors should be used throughout treatment with atezolizumab.

¹² Serum Chemistry to include creatinine, glucose, total protein, blood urea nitrogen, total carbon dioxide, albumin, total bilirubin, alkaline phosphatase, and aspartate transaminase and/or alanine transaminase and electrolytes (total calcium, chloride, potassium, sodium).

¹³ Per atezolizumab package insert (Section 5.4 – Thyroid Disorders); Thyroid function should be monitored prior to and periodically during treatment with atezolizumab. Package insert and institutional practice should be followed throughout treatment with atezolizumab.

¹⁴ Immune Function Analysis sample will be collected every 3 cycles.

¹⁵ Atezolizumab is to be administered at a dose of 1200 mg as an intravenous infusion (over 30 minutes) on Day 1 every 3 weeks. ¹⁶ Obtain results from medical records when available.

¹⁷ Tumor biopsy for correlative studies including scoring of tumor infiltrating lymphocyte (TIL) and PD-1 / PD-L1 expression analysis will be obtained at any time when available.

CL-PTL-126 Page 52 of 60 It is the user's responsibility to verify adequate training before executing a document. Do not make unauthorized copies

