- Events suggestive of hypersensitivity, infusion-related reactions, cytokine release syndrome, influenza-like illness, systemic inflammatory response syndrome, and systemic immune activation
- Nephritis
- Ocular toxicities (e.g., uveitis, retinitis)
- Myositis
- Myopathies, including rhabdomyolysis
- Grade \geq 2 cardiac disorders (e.g., atrial fibrillation, myocarditis, pericarditis)

Criteria for Hy's Law (FDA Guidance 2009)

- The drug causes hepatocellular injury, generally shown by a higher incidence of 3-fold or greater elevations above the ULN of ALT or AST than the (non-hepatotoxic) control drug
- Among trial subjects showing such aminotransferase elevations, often with aminotransferases much greater than 3 x ULN, one or more also show elevation of serum total bilirubin to >2 x ULN, without initial findings of cholestasis (elevated serum alkaline phosphatase)
- No other reason can be found to explain the combination of increased aminotransferases and total bilirubin, such as viral hepatitis A, B, or C; pre-existing or acute liver disease; or another drug capable of causing the observed injury.

Unexpected Adverse Event

An unexpected event is any AE that is not identified in nature, severity or frequency in the Clinical Investigator's brochure or the drug package insert.

Grading Adverse Events

Adverse events (AEs) will be recorded throughout the trial. Toxicities and AEs will be graded and reported using the Common Toxicity Criteria for Adverse Events (CTCAE) Version 4.03 as linked in Appendix D.

Adverse events will be summarized using the MedDRA coding system or higher. The NCI-CTCAE will be used for AE grading. All AEs, regardless of severity, will be followed by the Treating Physician until resolution is satisfactory.

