14.5 Recording of an Adverse Event

Adverse events will be recorded for the duration of a subject's study treatment (following the first dose of Investigational Product, Vigil and/or atezolizumab), and for up to 30 days following the last study treatment or until another therapy has been initiated, whichever is earlier, regardless of causality.

SAEs and AESIs should be recorded for the duration of the study treatment and for up to 30 days following the last study treatment or the initiation of new therapy, whichever is earlier.

All AEs, regardless of causal relationship are to be recorded in the eCRF and source documentation. Additional information about each event, such as treatment required, eventual outcome, and whether or not therapy had to be interrupted or dosages reduced, will be noted in source documents and recorded on the eCRF.

Pre-existing conditions will be recorded at baseline on the Medical History Form. If a preexisting condition does not change, it does not have to be reported as an AE on subsequent cycles.

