16.0 STATISTICAL CONSIDERATIONS

16.1 Safety Analysis

The safety evaluation will include AEs, AESIs, SAEs, and changes from baseline in laboratory evaluations, vital signs, electrocardiograms, and physical examinations. The number and percentage of subjects reporting treatment emergent AEs will be summarized overall and by the highest Common Terminology Criteria for Adverse Events (CTCAE) grade, system organ class, and preferred term, with a breakdown by dose and tumor type. Similarly, the number and percentage of subjects reporting treatment-emergent AEs considered related to investigational product will be summarized. At each level of subject summarization, a subject will be counted once using the highest grade and level of causality if one or more occurrences of the same system organ class/preferred term is reported. Adverse events will be graded according to the National Cancer Institute (NCI) CTCAE v4.03 and coded using the Medical Dictionary for Regulatory Activities. Laboratory abnormalities will be graded according to the NCI CTCAE v4.03, if applicable.

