APPENDIX B: SCHEDULE OF ASSESSMENTS

1 cycle = 3 weeks	Pre-Study ¹	Screening	Cycle 1	Cycle 2	Cycles 3, 6, 9, 12	Cycles 4, 5, 7, 8, 10, 11	EOT (30 days) ²	Response Follow-Up (quarterly) ³	Survival (3 years) ⁴
Visit Window		-2 weeks			±5 days			+/- 7 days	±4 weeks
Informed Consent	Х	within 4 weeks							
Medical History	Х	X							
Physical Exam	Х	X					Х		
Symptom-Directed Physical Exam ⁵			Х	Х	Х	Х	Х		
Performance Status (ECOG)		X	Х	X	Х	Х	Х		
Vital Signs (including weight) ⁶	Х	X	Х	X	Х	Х	Х		
Toxicity (adverse events)			Х	X	Х	Х	Х		
Concomitant Medications		x	х	x	Х	Х	Х	X ⁷	X ⁸
Radiological Tumor Assessment ⁹		within 4 weeks			X ¹⁰		X ¹¹	х	
Triplicate Electrocardiogram (ECG)		X			Х		Х		
CBC with differential	Х	X	Х	X	Х	Х	Х		
Serum Chemistry ¹²	Х	X	Х	X	Х	Х	Х		

CL-PTL-126 Page 50 of 60

Confidential and proprietary information of Gradalis, Inc.

Version: 04 Effective: 26-SEP-2018

It is the user's responsibility to verify adequate training before executing a document. Do not make unauthorized copies

¹ Pre-Study assessments including medical history, physical exam, CBC and Serum Chemistry may be obtained from medical records from standard preoperative hematology and chemistry panels.

² End of Treatment visit will occur 30 days (+ 5 days) after the last treatment or prior to commencement of subsequent treatment.

³ Subjects that discontinue study treatment before disease progression will have radiological assessment of disease quarterly until disease progression.

⁴ Assessment performed annually after disease progression.

⁵ Symptom-Directed Physical Exam performed by a medical provider.

⁶ Vital signs (including weight) must be obtained predose. Vital signs (heart rate, respiratory rate, blood pressure, temperature, and O₂ saturation) should also be obtained within 60 minutes prior to each atezolizumab infusion.

⁷ Collect any post study therapies taken after participation in the study.

⁸ Collect any post study therapies taken after participation in the study.

⁹ Radiological Tumor Assessment to include chest, abdomen, and pelvis. Assessment will be done per RECIST criteria for measurable disease.

¹⁰ Radiological Tumor Assessment will be performed at baseline and every third cycle thereafter.

¹¹ Radiological Tumor Assessment performed at End of TX if not done within the previous 45 days.

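### Appendix C lists AESIs and SAEs in place of all AEs for Part 3, contradicting section 14.5; if sites follow it, late non-serious AEs drop out of the 16.1 tables

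*Combined protocol and SAP*

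**What the plan says.** Two schedules govern safety collection. Appendix B, which covers Cycles 1 to 12 and the end-of-treatment visit, has the row "Toxicity (adverse events". Appendix C, which covers Part 3, has instead "Toxicity (AESI/SAEs", marked for each cycle and for end of treatment.

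The body text has one rule for the whole study. Section 14.5 states: "Adverse events will be recorded for the duration of a subject's study treatment", continuing for up to 30 days after the last treatment or until another therapy starts, and adds: "All AEs, regardless of causal relationship are to be recorded in the eCRF and source documentation". Section 14.0 states: "Adverse events (AEs) will be recorded throughout the trial". Section 5.6 and the synopsis give the same span, from first dose through treatment and follow-up. None of these makes an exception for Part 3.

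On analysis, section 16.1 states: "The number and percentage of subjects reporting treatment emergent AEs will be summarized overall and by the highest Common Terminology Criteria for Adverse Events" grade, system organ class and preferred term, "with a breakdown by dose and tumor type". Each subject is counted once, at the highest grade. The section gives no breakdown by Part, period or regimen and no window for what counts as treatment-emergent.

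**The concern.** The schedule and the body text tell a site to record different things in Part 3. Sites work from schedules and from the case report forms built on them, so the Appendix C row may well be what is applied, and practice may differ between sites.

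Under Appendix C, a non-serious event outside the AESI class that begins or worsens after Cycle 12 leaves no record. Section 16.1 then cannot distinguish that subject from one who had no event. This could include a non-serious Grade 3 event, which would otherwise set the subject's worst grade. Two reactions for which section 6.2.2 requires dosing to be held, Grade 3 rash and symptomatic hypothyroidism, are not named in the section 14.0 list of AESIs.

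Safety is the primary objective. Part 3 subjects have come through the combination cycles, so late events after combination exposure are part of the profile the trial sets out to describe. Part 3 can run until progression, so the narrower collection has no fixed end.

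**Working it through.** The plan states no figure to reproduce: section 16.3 says the sample size has no statistical basis, and neither an AE rate nor a Part 3 headcount is given. The check is a comparison of texts followed by an illustration on stated assumptions.

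**1. Scope of collection, side by side**

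| Source | Period | What is recorded |
|---|---|---|
| Appendix B | Cycles 1-12 and end of treatment | All AEs |
| Appendix C | Part 3 cycles and end of treatment | AESIs and SAEs |
| 14.5 | All study treatment, plus up to 30 days | All AEs |
| 14.0, 5.6, synopsis | Throughout treatment and follow-up | All AEs |

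Appendix C is the only source that narrows the scope, and no text explains why. The narrowing starts after 12 × 21 = 252 days of scheduled treatment.

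**2. Which events are exposed.** Three conditions must all hold: the event is non-serious, it is outside the AESI class, and it is new or of higher grade in Part 3. Because a subject is counted once at highest grade, a repeat at the same or lower grade changes nothing in the tables.

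**3. Direction.** Following Appendix C can remove a qualifying event but cannot add one. The bias in late incidence and worst grade is therefore downward or zero, and it is zero if 14.5 is followed.

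**4. Size, as an illustration.** Let
- N = subjects enrolled, 20 or 25 (section 5.1);
- f = share entering Part 3, assumed 10% to 40%;
- q = share of those whose first or worst-grade event of a given kind is a non-serious, non-AESI event in Part 3, assumed 10% to 30%.

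Subjects missed = N × f × q. Loss in percentage points = 100 × f × q. Chance of missing at least one subject = 1 − (1 − f × q)^N.

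| N | f | q | Subjects missed | Percentage points | Chance of at least one |
|---|---|---|---|---|---|
| 20 | 0.10 | 0.10 | 20 × 0.01 = 0.2 | 1 | 1 − 0.99^20 = 18% |
| 20 | 0.20 | 0.30 | 20 × 0.06 = 1.2 | 6 | 1 − 0.94^20 = 71% |
| 25 | 0.20 | 0.30 | 25 × 0.06 = 1.5 | 6 | 1 − 0.94^25 = 79% |
| 25 | 0.40 | 0.30 | 25 × 0.12 = 3.0 | 12 | 1 − 0.88^25 = 96% |

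**5. Where a table cut would fall.** If both agents are given on Day 1 of Cycle 12, the first Part 3 cycle starts about 21 days later. Ending the all-AE tables at the start of Part 3 would stop 30 − 21 = 9 days short of the 30-day window in 14.5. It would also discard any Part 3 events that sites did record under 14.5.

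**The case against.** The strongest reply is that the body text is clear, repeated and without exception, and that Appendix C does not expressly exclude other AEs. On that view this is a labelling slip and no data are lost. It stands to this extent: a reader might infer that late AEs are under-counted as an unavoidable result of the design, and the documents do not support that. Two instructions conflict, and loss follows only where the schedule row is applied over 14.5.

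The reply also has force on reach. The primary objective concerns the combination, whereas Part 3 is atezolizumab alone in sponsor-approved subjects with stable disease or better. Appendix B covers the combination cycles in full. In Part 3, SAEs are still collected, and so are detected AESIs, a class that section 14.0 introduces as open-ended. Blood counts, chemistry, vital signs and symptom-directed examinations also remain scheduled, and 16.1 grades laboratory abnormalities where applicable.

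Three further readings are tempting but go too far:
- **ECG and TSH.** Appendix C changes both from fixed visits to recommended ones. A reader might count this as another breach of 14.5, but 14.5 concerns AE recording and is silent on these tests. The footnotes still say that monitoring should follow institutional practice and, for thyroid function, the package insert.
- **Pooling.** A reader might take 16.1 to say that Part 3 is combined with earlier treatment. It does not say so; it neither separates Part 3 nor defines the treatment-emergent window.
- **Rates over time.** A reader might argue that AE rates per unit of exposure would fall artificially after Cycle 12. Section 16.1 plans no such rate. Cumulative-incidence sums for one subject on an assumed constant hazard likewise do not give a table percentage for 20-25 subjects.

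The contradiction survives all of this, as does the absence of any analysis rule that would contain its effect.

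**Conclusion.** The point holds in conditional form. The Appendix C Toxicity row contradicts sections 14.5, 14.0 and 5.6 and the synopsis. If it is followed, new or worsening non-serious, non-AESI events after Cycle 12 are counted as not having occurred, and 16.1 has no split that would reveal it.

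The true size is unknown. On the assumed ranges it is 0.2 to 3.0 of 20-25 subjects, or 1 to 12 percentage points for the affected kinds of event. Both input ranges are assumptions and neither comes from the documents.

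The effect on the primary objective is limited to late events after combination treatment. The point deserves correction because it decides which safety data are captured, and the correction is cheap. It does not undermine the safety data collected during Cycles 1 to 12.

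**What to change.** **Schedule.** Replace the Appendix C Toxicity row with the Appendix B label, "Toxicity (adverse events", so that it agrees with 14.5. If this is done before any subject enters Part 3, no loss arises from this source.

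**Analysis, for Part 3 data already collected under Appendix C.** Add to 16.1:
- The main all-AE and worst-grade tables run to 30 days after the last combination dose, or to the start of new therapy if earlier. For a subject who had both agents at Cycle 12, about the last 9 of those days fall under Appendix C, and a footnote should say so.
- Part 3 AEs appear in a separate table that keeps every event recorded, with a note that non-serious, non-AESI events may be incomplete there.
- Where Vigil ran out before Cycle 12, Appendix B still collects all AEs to Cycle 12, so the text should also say which table holds those later cycles.

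**Cost.** One schedule row, a few sentences in 16.1, and minor extra case report form entry at visits already held each cycle. No new procedure is needed.
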